3. Find the corresponding group below and follow the remainder of the instructions to complete Session 2.
 - a. AB- see #4 below
 - b. P- see #5 below
 - c. CD- see #6 below
 - d. Group designation is indicated by a post-it note the CTC placed inside the participant's Session 2 folder.
- 4. AB group hearing aid selection and fitting**
 - a. A1/A2 escorts participant to participant side of audio booth.
 - b. Turn chair and place within marks on the floor and position external speaker within marks on the floor for real-ear testing. Participant is seated in this chair for hearing aid programming.
 - c. Hearing aid color and dome choice
 - (1) Participant chooses hearing aid color. Audiologist chooses appropriate dome size and tubing length using hearing aid manufacturer's tubing measurement tool.
 - d. Program hearing aids
 - (1) Audiologist places Audiogram (1-6) on lap to be in view of the participant to

mimic what occurs in typical audiology clinic

- (2) Enter participant number and audiogram into Noah, then click Aventa in upper right corner.
 - (3) Connect hearing aid and generate first fit in the manufacturer's fitting software using NAL-NL2 fitting algorithm.
 - (4) Fitting should default to "Experienced Non-Linear".
 - (5) Select "Fitting" tab (top toolbar) and turn "Binaural Correction" off.
 - (6) Change "Physical Properties" to the size of dome and tube chosen.
 - (7) Change P1 to "Basic+Softswitching" if it is not already on that setting.
 - (a) Directionality: Fixed
 - (b) Directional Mix: Very Low
 - (c) DFS Ultra: Moderate
 - (d) Expansion: Off
 - (e) Noise Tracker II: Per Environment
 - (f) Wind Guard: Off
 - (8) Click on "Environmental Optimizer" and click "Reset to..." then select "0 dB" so that all levels are at zero.
 - (9) If applicable, click on "Tinnitus Sound Generator" and ensure it is off.
- e. Real-ear measurement on Verifit
- (1) Use Verifit to obtain real-ear measurements to verify hearing aids meet NAL-NL2 target output for speechmap.
 - (2) "Tests" → "On-ear measures" → "Speechmap"
 - (3) Enter participant's RECD measurements along with pure-tone air-conduction

thresholds.

- (4) Insert one probe tube in each ear.
 - (a) Check that the probe tube is connected to the appropriate R/L cord.
 - (b) Check that each reference microphone is facing outwards.
 - (c) Mute hearing aids prior to insertion.
 - (d) Choose “Open” as the hearing aid type on the Verifit.

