- (1) Run test box speechmap on hearing instruments following programming (right, then left) (open/close battery door following programming to disconnect from Aventa).
- (2) Audiograms and the RECD should still be entered from real ear measurements.
- (3) “Tests”→ “Test box measures”→ “Speechmap”
- (4) Couple hearing aid to ITE coupler using new strip of sticky tack (this will be used for their hearing aids only) keeping dome in place.
 - (a) Run speechmap for “carrot passage” at 65, 55 and 75 dB SPL input.
 - (b) Run MPO test.
 - (c) Record SII values for 65, 55, and 75 dB SPL stimuli on Session 2
Audiologist Checklist (2-1).
 - (d) Repeat with left hearing aid.
- (5) Change format settings to “Table”.
- (6) Select “Print”, enter file name, and press “Continue” to save to USB flash drive.
- (7) Save as an XML file
 - (a) Press “Session” on Verifit, then select “Store session to file”.
 - (b) Select the “Client ID” box and enter file name and press “Continue”. This will save file in “Sessions” folder on USB flash drive along with a style sheet (audioscan.xml).
- (8) Discard sticky tack.
- (9) Record hearing aid serial number, color, tubing and dome sizes on light blue Hearing Aid Decision Form for Audiologist (2-2).
- (10) Draw shade to block the view of the participant side of the booth.

- (11) Take participant to tester side of booth and tell him or her that A3 will be in shortly to complete the hearing aid orientation and answer any questions about hearing aid maintenance.
- (12) Leave hearing aids (without batteries inserted) in participant's hard case on tester side of the booth for A3.
- (13) Take participant's folder to CTC.
- (14) Notify A3 that participant is ready for orientation. Participant's guest may join him and her at this time (A3 will escort guest if applicable).
- (15) A1/A2 will transfer all (renamed) Verifit files from USB flash drive onto server in appropriate folders. Also transfer same files on USB flash drive into "USB dump file" on server.
- (16) Print the testbox speechmap for both ears and place in the Session 2 folder.

j. Hearing aid orientation

- (1) A3 completes hearing aid orientation (~45-60 minutes) covering each point on Orientation Checklist (2-3).
- (2) Inform participant that any additional questions that come up during the six-week trial period need to be directed to CTC.
- (3) A3 escorts participant to CTC's office after orientation is completed.

k. CTC does the following

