 - (4) Fitting should default to "Experienced Non-Linear".
 - (5) Select "Fitting" tab (top toolbar) and turn "Binaural Correction" off.
 - (6) Change "Physical Properties" to the size of tube and dome chosen.
 - (7) Change P1 to "Basic+Softswitching" if it is not already on that setting.
 - (a) Directionality: Fixed (Omni as of 5/5/2014)
 - (b) Expansion: Off
 - (c) Noise Tracker II: Per Environment
 - (d) Wind Guard: Off
 - (8) Click on "Environmental Optimizer" and click "Reset to..." then select "0 dB" so that all levels are at zero.
 - (9) If applicable, click on "Tinnitus Sound Generator" and ensure it is off.
- f. Real-ear insertion gain using Verifit
- (1) Prior to completing Verifit tests, enter zeros for audiogram thresholds and enter

participant's measured RECD into Verifit.

- (2) "Tests" → "On-ear measures" → "Insertion Gain" (65-dB-SPL pure tones)
- (3) Insert one probe tube in each ear.
 - (a) Check that the probe tube is connected to the appropriate right or left cord.
 - (b) Check that each reference microphone is facing outwards.
- (4) Select "Audiogram" and change "REUR" to "measure".
- (5) Measure REUR for both ears (probe tubes are only things in ears).
- (6) After REUR is measured in both ears, insert hearing aids and measure REAR using a 65 dB SPL tonal sweep for both ears.
- (7) Fine tune gain in software to make REIG response as close to zero as possible.
- (8) If REIG is too high: Use "Environmental Optimizer" settings to reduce REIG (these settings must change equally for all environments and can only be reduced down to a maximum of 6 dB).
- (9) If REIG is too low: use gain adjustment to increase gain at specific frequencies.
- (10) Change format settings to "Table".
- (11) Insert USB flash drive into Verifit USB port.
 - (a) Select "Print" and enter file name and press "Continue" to save to USB flash drive.
- (12) Disinfect both probe tubes with two disinfectant wipes, dry with paper towel, and place in envelope with participant # labeled on front.

g. Program VC

- (1) Click "copy" with "P1" (Program 1) gain settings visible.
- (2) Click on "P2" and click "paste".

- (a) Select “all” gain values on “P2” frequency gain response and increase overall gain +1 dB.
- (3) Click on “P3” and click “paste”.
 - (a) Do not make any gain changes to this program.
- (4) Click on “P4” and click “paste”.
 - (a) Select “all” gain values on “P4” frequency gain response and increase overall gain by +3 dB.
- (5) Return to “P1”.

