 - (a) Select “all” gain values on “P1” frequency gain response and increase overall gain +2 dB.
- (6) Before removing hearing aids, review “beeps” with participant by clicking on “Beeps and Volume Control” and presenting each beep sample (delayed start, low battery, and program change) and verifying that beeps are loud enough.
- (7) Click “Save” to save settings to hearing aids and to Aventa software (click “No” if a box pops up that prompts you to “use auto relate to apply gain adjustments from one program to the other programs”).

h. Final coupler measurements

- (1) Run test box speechmap with “carrot passage” input on hearing instruments following programming (right, then left) (open/close battery door following programming to disconnect from Aventa).
- (2) Audiogram and the RECD should still be entered from real ear measurements.
- (3) “Tests” → “Test box measures” → “Speechmap”
- (4) Couple hearing aid to ITE coupler using new strip of sticky tack (this will be

used for their hearing aids only) keeping dome in place.

- (a) Run speech at 65, 55 and 75 dB SPL input.
- (b) Run MPO test.
- (c) Record SII values for 65, 55, and 75 dB SPL stimuli on the Session 2 Audiologist Checklist (2-1).
- (d) Repeat with left hearing aid.
- (5) Change format settings to “Table”.
- (6) Select “Print” and enter file name and press “Continue” to save to USB flash drive.
- (7) Save as an XML file:
 - (a) Press “Session” on Verifit then select “Store session file”.
 - (b) Select the “Client ID” box and enter file name and press “Continue”. This will save file in “Sessions” folder on USB stick along with a style sheet (audioscan.xsl).
- (8) Discard sticky tack.
- (9) Record hearing aid serial number, color, tubing and dome sizes on light blue Hearing Aid Decision Form for Audiologist (2-2).
- (10) Draw shade to block the view of the participant side of the booth.
- (11) Take participant to testing side of booth and tell the participant that A3 will be in shortly to complete the hearing aid orientation and answer any questions about hearing aid maintenance.
- (12) Leave hearing aids (without batteries inserted) in participant’s hard case on tester side of the booth for A3.

- (13) Take participant's folder to CTC.
 - (14) Notify A3 that participant is ready for orientation. Participant's guest may join him or her at this time (A3 will escort the guest if applicable).

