2. On the Verifit, “Test Box Measures” → “Speechmap” (“carrot passage”)
3. Enter participant’s RECD and audiogram.
4. Run speechmap at 55, 65 and 75 dB SPL.
5. Run MPO test.
6. Record SIIs for 65, 55, and 75 dB SPL stimuli on the Hearing Aid Inspection Checklist (3-2).
7. Change format settings to “Table”.
8. Insert USB into Verifit.

9. Select "Print" and enter file name and press "Continue" to print to USB.
10. Repeat with the left hearing aid.
11. Save as an XML file:
 - a. Press "Session" on Verifit, then select "Store session file".
 - b. Select the "Client ID" box and enter file name and press "Continue" (refer to file naming nomenclature sheet in booth). This will save file in "Sessions" folder on USB stick along with a style sheet (audioscan.xml).
12. Listening check
 - a. Record the program hearing aids are in on checklist.
 - b. Record any abnormalities in hearing aid sound quality on checklist.
 - c. Record any hearing device deficiencies on checklist.
13. Open battery door and record battery condition on checklist (record action to fix battery condition on checklist if necessary).

E. HEARING AID MAINTENANCE (3-2)

1. Complete remaining portions of Hearing Aid Inspection Checklist (3-2) and record any maintenance performed.
2. Post-maintenance test box measures (same as was done on as-worn hearing aids)
 - a. Always re-run in test box even if no maintenance was needed.
3. Leave sticky tack on coupler for A4.
4. Record post-maintenance SIIs for 65, 55, and 75 dB SPL stimuli on Hearing Aid Inspection Checklist.
5. Select "Print" and enter file name and press "Continue" to print to USB.
6. Save as an XML file:

- a. Press “Session” on Verifit, then select “Store session file”.
 - b. Select the “Client ID” box and enter file name and press “Continue” (refer to file naming nomenclature sheet in booth). This will save file in “Sessions” folder on USB stick along with a style sheet (audioscan.xsl).
7. Give hearing aids to A4 with battery doors open.
 8. Print the post-maintenance simulated speechmap for both ears and give it to CTC to along with the As-Worn CST Form (3-1) and Hearing Aid Inspection Checklist to be placed in participant’s file.

F. AIDED PHAP (T-3), AIDED HHIE (T-4) AND HASS (HEARING AID SATISFACTION SURVEY) (T-5)

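### Placebo Session 2 SIIs are recorded with zero thresholds in the Verifit, so they are not comparable with AB Session 2 or with Session 3 (low severity)

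*Protocol*

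**What the plan says.** **Placebo, Session 2 (Protocol II.C.5).** Step f(1) reads "Prior to completing Verifit tests, enter zeros for audiogram thresholds and enter" the participant's measured RECD. The aids are then tuned towards zero insertion gain (f(7) to f(9)), and the volume-control programs are set (g). For the final test-box run, h(2) states: "Audiogram and the RECD should still be entered from real ear measurements". Step h(4)(c) puts the SIIs for 65, 55 and 75 dB SPL on the Session 2 Audiologist Checklist (2-1), and h(4)(d) repeats the run for the left aid.

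**AB, Session 2 (II.C.4).** Step e(3) enters the participant's "RECD measurements along with pure-tone air-conduction" thresholds. Step i(2) carries them forward in almost the same sentence: "Audiograms and the RECD should still be entered from real ear measurements". Step i(4)(c) records SIIs at the same three levels on the same checklist.

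**Session 3, all groups (III.D and III.E).** Step D.3 enters the participant's "RECD and audiogram", and D.6 says "Record SIIs for 65, 55, and 75 dB SPL stimuli on the Hearing Aid Inspection Checklist". The post-maintenance run (E.2) is done in the same way.

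**The concern.** The sentence at h(2) appears to have been carried across from the AB procedure. It works there because the real-ear step used the participant's true thresholds. In placebo the real-ear step used zeros, so the same sentence keeps the zeros in place while the SIIs are recorded.

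Zeros may well suit the tuning in f, where the aim is an insertion gain near zero whatever the hearing loss. No reason is given for keeping them in h. An audibility index computed against zero thresholds describes a listener with no hearing loss. Someone working from the checklist alone could not see this, and might take the placebo fitting to have been more audible than it was, or take a fall by Session 3 as real.

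For placebo, the h run is also the only Session 2 source of SII. AB has on-ear SIIs as well (C.4.e(7)), taken on true thresholds.

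**Working it through.** There is no stated figure to reproduce. The check is to follow which thresholds are in the Verifit each time an SII is recorded.

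| Step | Placebo, Session 2 | AB, Session 2 | Session 3, all groups |
|---|---|---|---|
| Thresholds entered | zeros, C.5.f(1) | participant's own, C.4.e(3) | participant's own, III.D.3 |
| Changed before the SII? | no | no | no |
| Instruction at the coupler run | keep the real-ear entries, h(2) | keep the real-ear entries, i(2) | entered at D.3; E.2 repeats the run |
| SII recorded | h(4)(c) | i(4)(c) | D.6; E.4 after maintenance |
| Thresholds behind the SII | **zeros** | **own audiogram** | **own audiogram** |

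Two placebo steps might seem to restore the true thresholds, but neither does:

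- C.5.e(2) enters the audiogram into Noah, the fitting software. It precedes f(1) and does not touch the Verifit.
- C.5.f(4) opens the audiogram screen only to set the unaided response to be measured.

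The CD group has no SII recorded in Session 2, so the contrast affected at that visit is placebo against AB.

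**Direction.** This assumes that the Verifit's SII depends on the thresholds entered and does not fall when they are lowered; the document does not describe the calculation. Eligible participants have mild to moderate loss (I.F.8), so zeros are better than their own thresholds over the affected frequencies. The placebo SII is then overstated.

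**Size.** This cannot be computed. The document gives no SII formula, no thresholds for individual participants and no aided output levels. An illustrative single-band model with assumed levels can be made to give anything from no overstatement to the whole scale, so it sets no bound and none is used here.

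**Number of values.** 3 levels × 2 ears = 6 recorded SIIs per placebo participant.

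**The case against.** The strongest reply is that nothing in the protocol depends on these values. SII is not named as an outcome, an eligibility test or a fitting criterion. AB fits are accepted on output within 4 dB, or at worst 7 dB, of target (C.4.e(5)), and placebo fits on insertion gain as close to zero as possible (C.5.f(7)). That is correct, and it keeps the severity low.

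A second reply is that the needed information exists elsewhere. Session 3 gives as-worn and post-maintenance SIIs on true thresholds before group is revealed and before any reprogramming. The Session 2 test-box results are stored as a table and an XML file (h(5) to h(7)). This largely stands. The Session 3 values describe the aids after about six weeks of wear, however, in whatever program D.12(a) records, so they are not an exact substitute for a record at fitting.

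A third reply is that h(2) was meant to call for the true audiogram. The wording points back to the real-ear entries, which were zeros. If the true audiogram was intended, staff still have no step telling them to re-enter it, and the same correction is needed.

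A reader might also infer that a single form field mixes the two bases. Checklist 2-1 is not shown, and AB supplies both on-ear and coupler SIIs to it, so the text supports only that both groups use the same checklist.

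**Conclusion.** The point holds in limited form. Followed as written, the protocol yields placebo Session 2 SIIs based on zero thresholds. They are overstated by an unknown amount and are not comparable with AB Session 2 or with Session 3. This rests on the step order above and on the assumption that SII depends on the thresholds entered. Severity is low.

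Two stronger readings are tempting and are not supported:

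- **That the placebo condition or the group comparisons are compromised.** The speech and questionnaire measures do not use these SIIs, no gain setting depends on them, and Session 3 SIIs on true thresholds are available to check placebo audibility.
- **That the placebo insertion-gain record is wrong because P1 is raised by 2 dB after it is saved.** The offset is explicit and fixed (C.5.g). The saved table documents the tuned setting, which P3 retains, and the coupler run follows the programming. That is not an error.

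**What to change.** **For re-use of the protocol.** Keep zeros for the tuning in C.5.f. Change h(2) so that the participant's audiogram replaces the zeros before h(4), with the RECD left as entered. The audiogram is already in the Session 2 folder (I.N.8). The participant stays in that part of the booth until h(11), and a display against true thresholds could show output below target, so the screen should be out of view. Alternatively, leave the bench procedure alone and compute the SIIs offline from Audiogram (1-6).

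**For data already collected.** Do not set the recorded placebo Session 2 SIIs beside AB or Session 3 values. If the files stored at h(5) to h(7) hold output by frequency, which the document does not say, recompute the SIIs with the participant's audiogram and keep the recorded values under a separate name. If they do not, label the recorded values as zero-threshold and use the Session 3 as-worn SIIs for group comparison.

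**Cost.** One re-entry of thresholds per placebo participant, or recalculation of six values each, or one data flag. No gain setting changes.
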